9.1.2 Clinically Relevant Non-major Bleeding

Clinically overt bleeding that requires treatment will be taken to be clinically relevant non-major bleeding. For example, this includes (but is not limited to) the following diagnostic tests and treatment. The definition of "requiring treatment" does not include outpatient examinations that do not involve the following medical procedures (diagnostic tests or treatment), or procedures similar to these. Clinically relevant non-major bleeding must be visually confirmed by tests or radiological imaging.

- Hospitalization or prolongation of existing hospitalization
- Laboratory tests
- Imaging tests
- Endoscopic tests, Colonoscopy tests, cystoscopy tests, bronchoscopy tests
- Nasal cavity packing
- Pressure hemostasis
- Ultrasound-guided compression for aneurysm
- Coil embolization
- Cardioactive therapy
- Surgery
- Interruption or discontinuation of the study drug at the instruction of a physician
- Change in concomitant therapy at the instruction of a physician (such as dose reduction or discontinuation of aspirin)

9.1.3 Minor Bleeding

Other overt bleeding events that do not meet the criteria for major bleeding or clinically relevant non-major bleeding will be taken to be minor bleeding (for example, epistaxis that does not require treatment).

All events other than the above (such as a decrease in hemoglobin without overt bleeding) will all be classified as "no bleeding event."

9.2 Definition of Adverse Events

An adverse event is any unfavorable or unintended sign (including abnormal laboratory findings or vital signs), symptom or disease by the examination at completion of study treatment (the final follow-up examination for subjects who continue the study treatment)

or the examination at discontinuation, that and which does not necessarily have to have a causal relationship to this study drug.

Symptoms or diseases occurring before the study treatment will be entered on case report forms as concurrent conditions, and will not be considered adverse events. However, if a concurrent condition becomes aggravated during the study treatment, it will be handled as an adverse event, and the day on which aggravation was found will be considered to be the onset date of the adverse event.

9.3 Definition of Serious Adverse Events

Serious adverse events are adverse events that meet any of the following criteria.

- Death
- Is life-threatening
- Requires inpatient hospitalization or prolongation of existing hospitalization
- Disability
- Risk of disability
- Serious equivalent to the above
- Resulting in congenital disease or anomaly in the next generation

9.4 Adverse Event Information to Be Reported

If an adverse event occurs during the period from the initiation of study treatment to the examination at completion of study treatment, the items shown in Table 9-1 will be surveyed and entered on documents such as the case report form. When symptoms are surveyed by medical interview, the question "Have you had any symptoms that concern you between your last visit and this visit?" will be asked, to elicit free responses from subjects. Medical interviews or question sheets about specific symptoms will not be used to check for adverse events.

^{‡‡‡‡‡:} For subjects withdrawn from study participation

Table 9-1 Information to Be Reported When an Adverse Event Occurs

Item of Information	Details to Report		
Details of adverse	Adverse event term and onset date		
event			
Action taken for adverse event	Details of study drug action taken and other action taken		
Outcome	Outcome type, day of outcome assessment, and date of resolution		
Outcome type	Recovered/ resolved	The adverse event has been resolved and the subject has recovered to the state before the adverse event occurred	
	Recovering/ resolving	The adverse event has been almost resolved and the subject has nearly recovered to the state before the adverse event occurred	
	Not recovered/ not resolved	The adverse event has not been resolved, and the subject is in a state similar to that when the adverse event occurred (unchanged)	
	Recovered/ resolved with sequelae/residual effect(s) present	The adverse event has been resolved, but the subject has sequelae	
	Fatal	This indicates that the investigators consider that the adverse event is related to the death, or that a relationship cannot be ruled out, and does not apply in cases where the death is due to a cause such as aggravation of the disease under study	
	Unknown	There is no information and the outcome is unknown	
Severity	Mild	Does not interfere with subject's usual function, and is easily tolerated	
	Moderate	Enough to cause interference with usual activity	
	Severe	Enough to cause inability to do usual activity	
Seriousness	Serious/nonserious		
Causal relationship	Relationship classification (based on the following relationship classification), reason for causal relationship assessment		
Relationship classification	Related Not related	The onset of the adverse event follows a reasonable temporal sequence from study treatment, and cannot be reasonably considered to be due to the subject's clinical state or other factors (e.g., disease under study, concurrent diseases, and concomitant medications), and a relationship with the study drug cannot be ruled out The onset of the adverse event follows a reasonable temporal sequence from study treatment, and is a known reaction to the drug under study or its chemical group, or can be explained by known pharmacology The onset of the adverse event does not follow a reasonable temporal sequence from study treatment, or	
		can be reasonably explained by the subject's clinical state or other factors (e.g., disease under study, concurrent diseases, and concomitant medications), and a relationship with the study drug can be ruled out	

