Thus, administration of edoxaban at 15 mg once daily is associated with a lower bleeding risk than the available oral anticoagulant warfarin or administration of edoxaban at 30 mg or 60 mg once daily, and from the efficacy standpoint, it is considered to be effective at reducing the risk of stroke to a certain extent. Therefore, it is considered that 15 mg of edoxaban once daily can be administered to elderly patients with AF who have not received aggressive anticoagulant therapy due to concerns about bleeding. Accordingly, we planned a randomized, double-blind, placebo-controlled study to evaluate the efficacy and safety of administration of edoxaban at 15 mg once daily in elderly patients with NVAF who are ineligible for the standard of care, oral anticoagulants, at the approved dosage due to concerns about bleeding. A composite of stroke and SEE was selected for primary efficacy endpoint, to evaluate the superiority of administration of edoxaban at 15 mg once daily in reducing the risk of stroke and SEE compared to the placebo group. Major bleeding was selected for the primary safety endpoint, and compared with the placebo group, and clinical acceptability was also assessed with reference to the incidence of major bleeding with available oral anticoagulant therapies. If this study finds that administration of edoxaban at 15 mg once daily is effective, and that its safety is clinically acceptable, it is expected to provide a new option for stroke prevention in elderly patients with NVAF who have not received aggressive treatment with standard of care.

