4.2.1.2 Follow-up Survey During Study Drug Interruption

The investigator or subinvestigator will survey the following items until the examination at completion of study treatment or until the resumption of treatment at the visit specified in "6. STUDY PROCEDURES" at least every 8 weeks at a visit or by telephone, and will enter the information on the case report form. If the subject cannot be contacted by

telephone, surveys will be performed by letter.

- 1) Whether any serious adverse events have occurred
- 2) Whether any efficacy events have occurred
- 3) Whether any bleeding events have occurred
- 4) Whether any of the following drugs (including over-the-counter drugs) have been used: anticoagulants, thrombolytic drugs, antiplatelet drugs, intravenous antiarrhythmic drugs, or acidic NSAIDs
- 5) Blood pressure and pulse rate (only if the subject makes a visit)
- 6) Laboratory tests determined to be appropriate by the investigator or subinvestigator (only if the subject makes a visit). However, if warfarin is being administered, measurement of PT-INR is mandatory.

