9.1 Bleeding Events

Bleeding-related adverse events observed between the initiation of study treatment and the examination at completion of study treatment or the examination at discontinuation the discontinuation will be assessed as bleeding events. Bleeding events will be reassessed by a Clinical Bleeding Event Committee independent of the assessment of the investigator or subinvestigator, and the assessment of the Clinical Bleeding Event Committee will be taken as the final assessment.

Bleeding events will be classified into major bleeding, clinically relevant non-major bleeding, and minor bleeding according to the following definitions. Detailed definitions of bleeding events are shown separately in "Procedures for the Clinical Bleeding Event Committee."

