11.6 Planned Sample Size

Four hundred subjects in each group, for a total of 800 subjects

<Rationale>

In this study, 65 primary endpoint events observed in the ITT analysis set between randomization and the examination at completion of study treatment will be collected. Under the conditions that the annual incidence in the placebo group is 5%/year, the hazard ratio of DU-176b relative to the placebo group is 0.5, the significance level is 5%, 2-tailed, and the power is 80%, the number of events required to evaluate the superiority is 65. Assuming that the duration of the subject enrollment period is 2 years and the duration of the follow-up period is 1.5 years, it is estimated that approximately 400 subjects will be enrolled in each group. Thus, the planned sample size will be a total of 800 subjects. This study is an event-driven study, and the total number of subjects may change as necessary depending on the number of target events collected.

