15.3 Informed Consent

Before performing the examinations specified in the protocol for this study, the investigator or subinvestigator will explain the following information to the subject (and also to the legally acceptable representative, if the legally acceptable representative will provide consent) in an easily understandable way using the informed consent form, and obtain the subject's written informed consent to participate in the study, given of the subject's own free will. When obtaining informed consent, the investigator or subinvestigator will give the subject (or legally acceptable representative) ample time to decide whether or not to participate in the study, and will provide an opportunity to ask questions, and will provide thorough responses to these questions. As the subjects of this study will be patients with NVAF aged 80 years or older, more than a few of the patients will have dementia as a concurrent condition, and therefore, if the investigator or subinvestigator considers that it is not feasible to obtain written consent from the subject in person due to deterioration of cognitive function, the investigator or subinvestigator will also explain the study to a legally acceptable representative and obtain written consent, given of the legally acceptable representative's own free will. A legally acceptable representative is a person who is authorized to provide consent on behalf of a subject, and will be the subject's spouse, guardian, other caregiver, or other similar person, who is likely to act in the best interests of the subject, given the living circumstances and emotional relationship of the two people.

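### Section 9.4 bars specific symptom questions, and no direct bleeding or efficacy question is written for on-drug visits, so minor and clinically relevant non-major bleeding may be under-recorded

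*Combined protocol and SAP*

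**What the plan says.** Protocol 9.4 (Adverse Event Information to Be Reported) says that when symptoms are surveyed by interview, the subject is asked one open question about concerning symptoms since the last visit. It then states: "Medical interviews or question sheets about specific symptoms will not be used to check for adverse events". No caregiver is mentioned there.

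Section 9.1 defines the bleeding endpoints, including the primary safety endpoint, as "Bleeding-related adverse events observed between the initiation of study treatment and the examination at completion of study treatment" or, for subjects withdrawn from participation, the examination at discontinuation. Sections 6.14 (Efficacy Events) and 6.15 (Bleeding Events) refer to 9.4, but each begins only once an event has occurred.

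Off drug the text differs. Section 4.2.1.2 (interruption) lists "Whether any bleeding events have occurred" and a matching efficacy item, to be surveyed at least every 8 weeks. Section 4.2.2.2 (discontinuation) repeats both items.

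On the population, 15.3 expects that "more than a few of the patients will have dementia as a concurrent condition". On the use of the results, the Introduction says of major bleeding that "clinical acceptability was also assessed with reference to the incidence of major bleeding with available oral anticoagulant therapies".

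**The concern.** An open question finds what the subject remembers and is worried by. A nosebleed that was packed and forgotten, a bruise, or a mild deficit that has cleared may not be mentioned, least of all by a subject with dementia. If sites follow 9.4 as written, they may not then ask about bleeding by name.

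Two things are at stake:

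- **Absolute rates.** Blinding protects the comparison between arms. It does not protect a bleeding rate that is read on its own.
- **Detection that depends on drug status.** The primary analysis counts events whether or not the subject is taking study drug (11.4.2.1.1). The safety period runs from first dose to the completion examination (11.4.5). On-drug and off-drug time are therefore pooled. Whether a subject is on drug is decided after randomization and may follow a bleed: 9.1.2 lists interruption of study drug among the forms of treatment that make a bleed clinically relevant.

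**Working it through.** **1. The two periods side by side**

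| | On drug | Off drug |
|---|---|---|
| Direct bleeding or efficacy item | None written; 6.14 and 6.15 start once an event has occurred | Required (4.2.1.2, 4.2.2.2) |
| Contact | Visits every 4 weeks to Week 48, then every 8 | At least every 8 weeks, by visit or telephone, otherwise by letter |
| Laboratory tests | Every 8 weeks (6.8) | Investigator's choice, only at a visit |
| Other records | Examination or interview at each visit and an efficacy/bleeding row (Table 6-1); concomitant drugs, surgery, hospitalization (6.4, 6.10, 6.11) | Use of listed drugs; serious adverse events |

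The on-drug routes have gaps for lesser bleeding. A hemoglobin fall without overt bleeding is classed as no bleeding event (9.1.3). Clinically relevant non-major bleeding can be treated without admission, for example by packing or compression (9.1.2). Outside physicians are contacted about an event that is already known. The two committees reassess events, but no search for unreported ones is described.

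**2. The plan's own figure**

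The inputs in 11.6 are "the annual incidence in the placebo group is 5%/year" and "the hazard ratio of DU-176b relative to the placebo group is 0.5", and the stated result is: "the significance level is 5%, 2-tailed, and the power is 80%, the number of events required to evaluate the superiority is 65".

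Schoenfeld: events = (1.960 + 0.842)² / (0.25 × (ln 0.5)²) = 7.85 / 0.1201 = 65.35. Power at 65 events is 79.8%. The figure reproduces, and this point does not make it wrong.

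**3. Equal under-detection in both arms** (detection s is assumed)

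Both observed rates are multiplied by s, so HR = 0.025s / 0.05s = 0.5, and power at 65 events stays at 79.8%. What changes is timing. Expected events per arm, with 400 subjects, 2 years of uniform accrual, 1.5 years of follow-up and no dropout, are 400 × [1 − (e^(−1.5λ) − e^(−3.5λ)) / (2λ)], with λ = 0.05s or 0.025s:

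| s | Events at 3.5 years | Follow-up after last enrollment for 65 events |
|---|---|---|
| 100% | 71.0 | 1.28 years |
| 90% | 64.3 | 1.53 years |
| 80% | 57.5 | 1.84 years |
| 70% | 50.5 | 2.25 years |

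This applies s to every primary event. Only mild strokes are plausibly missed, so it overstates the delay.

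**4. Under-detection on drug only**

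Let f be the share of time off drug. Assume full detection and HR 1 off drug, and HR 0.5 on drug. Then observed HR = [0.5(1 − f)s + f] / [(1 − f)s + f].

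- f = 0.1: s = 1 gives 0.55; s = 0.8 gives (0.36 + 0.10) / (0.72 + 0.10) = 0.561. Power at 65 events goes from 67.4% to 64.4%.
- f = 0.2: s = 1 gives 0.60; s = 0.8 gives (0.32 + 0.20) / (0.64 + 0.20) = 0.619. Power goes from 54.0% to 48.9%.
- Unequal time off drug, s from 1 to 0.8: 30% on DU-176b against 20% on placebo moves the HR from 0.65 to 0.69; 20% against 30% moves it from 0.60 to 0.605.

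The step from 0.50 to 0.60 is dilution from assuming no effect off drug. Only the step from 0.60 to 0.62 belongs to detection.

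**5. Bleeding**

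The documents give no rate for minor or clinically relevant non-major bleeding, so the loss can be stated only as a proportion: at detection s, a share 1 − s of on-drug events is lost. For major bleeding, 5.2.1 gives 1.99%/year on 15 mg at age 80 or older. The formula in step 3 then gives 19.4 subjects in the DU-176b arm at full detection and 15.6 at 80%. That is an outer illustration, because major bleeding is the class least likely to be missed.

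**The case against.** The strongest reply is that detection on drug does not rest on the scripted question. The routes in the first table are all in the protocol. Efficacy and bleeding events have their own row in Table 6-1, separate from adverse events. This stands: a reader might infer that one open question is the only means of detection, and the documents do not support that.

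Next, 9.4 governs reporting of adverse events, and 6.14 refers to it for the details to record. A reader might infer that the bar certainly extends to stroke, systemic embolism and TIA. The text leaves that open. For bleeding there is no such doubt, because 9.1 makes it an adverse event by definition.

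Third, off-drug contact may be by telephone or letter with few tests, so it is not established that the off-drug state detects more overall. That stands too. What is established is that a direct item is required in one state and not written for the other.

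Fourth, clinical acceptability is judged on major bleeding, which by definition is fatal, at a critical site, or transfused with a hemoglobin fall. Such events leave records. TIA is only a descriptive endpoint and does not count toward the 65 events.

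Finally, prompts at each visit may sit in the case report form guide named in 15.9.2, which is not among the documents. If so, they would need to be squared with 9.4. Nothing in 9.4 forbids caregiver input, but nothing asks for it.

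**Conclusion.** The point holds as a gap in ascertainment, chiefly for minor and clinically relevant non-major bleeding and possibly for mild stroke or TIA. Sites that follow 9.4 as written may record fewer of these events on drug, and the method of finding them changes with drug status.

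Its size is unknown. The detection levels and off-drug shares used above are assumptions. Under them the primary hazard ratio is little affected: unchanged with equal under-detection, about 0.60 to 0.62 at 80% on-drug detection and 20% of time off drug, and at most 0.65 to 0.69 in the unequal cases tried.

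Two stronger readings are not supported. One is that major bleeding will be materially understated, so that the drug looks safer than it is; that class is the best covered by other records. The other is that ascertainment will differ between arms. The trial is double-blind, and the documents do not show that one arm will spend more time off drug. Nor do they say that many subjects will have dementia: the wording is more than a few, with no figure.

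**What to change.** - **9.4:** limit the bar on specific questions to adverse events other than bleeding and efficacy events. Keep the open question for everything else.
- **6.14 and 6.15:** require the existing efficacy and bleeding items of 4.2.1.2 to be asked at every on-drug visit, in the same words in both arms. Ask the caregiver or legally acceptable representative as well when the subject has cognitive impairment.
- **Case report form guide:** check that any visit prompts agree with the amended text.

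The cost is protocol wording, a few minutes per visit, and a somewhat higher reported count of minor bleeding in both arms. If the change is made while the study is running, record the date it takes effect, since absolute rates before and after it will not be collected in the same way.

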9.5 Definition of Adverse Drug Reactions

Adverse events for which the relationship with the study drug is considered to be "related" will be treated as adverse drug reactions.

9.6 Action When an Adverse Event Occurs

9.6.1 Action When an Adverse Event Occurs

If an adverse event occurs, the investigator or subinvestigator will take suitable action, and report to the Sponsor if necessary, and, as far as possible, observe the subject's course (even after the end of the specified observation period) until the adverse event is resolved to the state before onset or is resolving. However, even if the adverse event is not resolved and is not resolving, observation will be ended in the study, after an explanation is provided to the subject (or legally acceptable representative) if it can be considered that the subject's condition is stable and the subject's safety is ensured (however, treatment for the relevant symptoms will continue).

9.6.2 Action When a Serious Adverse Event Occurs

If a serious adverse event occurs, the investigator or subinvestigator will take suitable action, and will promptly report the details of the event to the Sponsor by telephone or fax. The investigator will promptly report these details in writing to the Sponsor and the director of the study site. The written report to the director of the study site will follow the procedure and format for the study site. This action will be taken until the final follow-up examination.

10. OTHER ENDPOINTS

10.1 Pharmacodynamics (Pharmacodynamic Indicators and Biomarkers)

At Week 8 of the study treatment period (Visit 3), PD indicators (PT and aPTT) and biomarkers (D-dimer and F1+2) will be assessed.

11. STATISTICAL ANALYSES

This is an overview of the statistical analysis. A more detailed description of analytical methods will be specified in the Statistical Analysis Plan.

11.1 Objective of Analysis

To evaluate the superiority of 15 mg of DU-176b compared to placebo, with regard to the

composite primary efficacy endpoint of stroke and SEE.

11.2 Analysis Sets

After case report forms have been locked, and before unblinding, the Sponsor will decide on the handling each subject, after discussion with the medical experts if necessary. After receiving advice from the medical experts, the Sponsor will decide on the handling of subjects not specified in the protocol.

The major efficacy analysis set will be the intent-to-treat (ITT) set, but analysis of the modified intent-to-treat (mITT) set and per protocol set (PPS) will also be conducted as sensitivity analysis.

